- a Evaluation assessments should be performed prior to administration of IMP unless otherwise indicated. Results should be reviewed by the Investigator prior to the administration of the next dose. All visits should occur within 3 days of scheduled visit unless otherwise noted.
- b Screening must occur within 28 days of dosing. The following procedures must be repeated at the day 1 visit: Medical and cancer history, physical examination, weight measurement, vital signs, hematology (see h), serum chemistry panel (see h). Lab values must still meet eligibility criteria on cycle 1, day 1. Tumor assessments must be repeated at the baseline visit only if determined to be changed by clinical exam or other clinical observations. SOC procedures performed prior to consent but within the protocol defined screening window for each assessment can be used for study purposes. All research only procedures must be performed after the consent date.
- c Patients may continue with daily dosing of enzalutamide with or without taselisib in the absence of unacceptable toxicities after C2 (or if the toxicity has resolved) and with no clinical evidence of disease progression.
- d The 30-day follow-up assessments should be done 30 (±3 days) days after the last dose of enzalutamide and taselisib. 30 day follow-up can be done by phone or by a clinic visit. Any ongoing toxicities should be documented. Any ongoing serious adverse events will be followed every 3 months until resolution. Any AEs or SAEs considered possibly or probably related to IMP that have not stabilized, returned to baseline, or are considered irreversible will continue to be monitored as per the protocol in Section 7.
- e MRI should be completed only if CT is unclear and a lesion can only be followed on MRI imaging. The CT scan should be completed with contrast. This is considered a research procedure if the patient does not have any signs or symptoms of brain metastases. If the patient must undergo brain imaging for the sole purpose of screening for this study, it is expected that a CT of the head will be done.
- f The physical examination will include measurements of height and weight at screening. Weight will be measured on day 1 of each cycle and at the End-of-treatment visit. Physical examination will include examination of major body systems including neurologic, cardiac, respiratory, gastrointestinal, and skin. Clinically relevant signs and symptoms will be reported as AEs.

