- g ECG will be performed at screening
- h Clinical laboratory tests will include hematology and serum chemistry panel including white blood cell count, differential, hemoglobin, platelet count, sodium, potassium, chloride, bicarbonate, BUN, creatinine, glucose, calcium, and magnesium, SGOT, SGPT, and total serum bilirubin, albumin, and total protein. Additional tests will be performed when clinically appropriate. In case of Grade 3 or higher abnormal liver function results, additional testing will be done weekly until recovery to baseline value (see section 7.2). For all other timepoints, labs can be performed up to 3 days prior to each timepoint indicated in the study calendar (other than required C1D1 timepoint). Results from labs obtained on C1D1 do have to meet eligibility criteria.
- i FPG (fasting plasma glucose) will be collected at screening, on Days 1 and 15 of C1, on CXD1 of subsequent cycles, and at the End-of-treatment visit. FPG will also be monitored if patients experience Grade ≥1 hyperglycemia during the course of the study per the hyperglycemia management guidelines provided in the protocol. FPG can be obtained up to 3 days prior to each timepoint indicated in the study calendar (other than required C1D1 timepoint). Fasting plasma glucose is the same as serum glucose on days that the patient is fasting. On days the patient is getting non-fasting labs, it should be serum glucose only. (See Table 3 under section 7.2.1.5)
- j Serum pregnancy test: women of child bearing potential must have a negative serum pregnancy test result within 28 days prior to the initial dose of IMP.

- k PKs for patients in the phase Ib portion: plasma sample should be obtained on Cycle 1, day 8 at: 0-4 hours prior to dose of taselisib and 1, 3, and 6 hours post administration taselisib. On Cycle 2, day 15 at: 0-4 hours prior to dose of taselisib and enzalutamide and 1, 3, and 6 hours post administration taselisib and enzalutamide. On Cycle 4, day 1, plasma sample should be obtained 0-4 hours before taselisib and enzalutamide administration, and 3 hours post-administration of both drugs. PKs in phase II will occur for 10 patients at the Vanderbilt site only and should be obtained on patients receiving both enzalutamide and taselisib: C2D1, C2D15, and C4D1 at 0-4 hours prior to taselisib and enzalutamide and 2 to 4 hours post treatment.

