- 4.1.11** Phase II only: Biopsy of a metastatic lesion in patients with reasonably accessible metastatic lesions (chest wall, skin, subcutaneous tissue, lymph nodes, skin, breast, bones, lung, and liver metastases). If a reasonably accessible metastatic lesion is not available, the patient may go on study provided that archived tissue is available. However, if a reasonably accessible site is available for biopsy, the patient must agree to biopsy. Any patients not undergoing biopsy must be approved for study enrollment by the Protocol Chair. Biopsies may be done with local anesthesia or intravenous conscious sedation, according to institutional guidelines. If a biopsy requires general anesthesia, then it is only allowed if acquisition of tissue is clinically indicated, and excess tissue may be collected for research purposes. Patients without sites available for biopsy must have available tissue [archived formalin-fixed paraffin embedded blocks (FFPB) or fresh frozen tissue from original diagnosis or metastatic setting] for correlative studies per Section 9.2.

Tissue needs to be located and available at the time of registration (tissue needs to be submitted within 3 weeks of study initiation).

**4.1.12** Patients must have adequate hematologic, hepatic, and renal function. All tests must be obtained within 28 days of starting treatment. Labs are to be repeated on C1D1 and must still meet eligibility. These include:

- ANC  $\geq 1500/\text{mm}^3$
- Platelet count  $\geq 75,000/\text{mm}^3$
- HgB  $\geq 9$  g/dL
- Creatinine  $\leq 1.5X$  upper limits of normal (ULN)
- INR  $\leq 2$
- Total serum bilirubin  $\leq 1.5$  x ULN (in patients with known Gilbert Syndrome, a total bilirubin  $\leq 3.0$  x ULN, with direct bilirubin  $\leq 1.5$  x ULN)
- AST and ALT  $\leq 3$  x ULN (or  $\leq 5.0$  x ULN if hepatic metastases are present)
- For patients without known Type II diabetes, the following is required at screening:
  - Fasting plasma glucose  $\leq 160$  mg/dL (7.49 mmol/L) and glycosylated hemoglobin (HbA1c)  $< 7.5$  % or International Federation of Clinical Chemistry (IFCC)  $< 53$  mmol/mol
- For patients with Type II diabetes receiving only oral anti-hyperglycemic therapy (patients receiving insulin are not eligible), the following are required at screening:
  - HbA1c  $< 8.5$  % or IFCC  $< 69.4$  mmol/mol
  - Stable regimen of oral anti-hyperglycemic therapy without insulin usage for at least 3 weeks prior to first study treatment

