  - Fasting plasma glucose levels  $\leq 160$  mg/dL (8.88 mmol/L) and no hypoglycemia (BS  $< 60$ ) during home monitoring for at least 1 week prior to study entry

**4.1.13** Patients must be able to swallow and retain oral medication.

**4.1.14** For patients who are not postmenopausal or surgically sterile (absence of ovaries and/or uterus), agreement to remain abstinent or to use two adequate methods of contraception (e.g., condoms, diaphragm, vasectomy/vasectomized partner, tubal ligation), during the treatment period and for at least 30 days after the last dose of study treatment or 3 months after discontinuation of taselisib and/or enzalutamide, whichever is longer. Hormone based oral contraceptives are not allowed on study. Postmenopausal is defined as:

- Age  $\geq 60$  years
- Age  $\leq 60$  years and amenorrheic for 12 months in the absence of chemotherapy, tamoxifen, toremifene, or ovarian suppression; or follicle stimulating hormone and estradiol in the postmenopausal range

**4.1.15** Patients may have received radiation therapy to painful bone metastases or areas of impending bone fracture as long as radiation therapy is completed  $\geq 2$  weeks prior to day 1 of cycle 1 of treatment. Patients who have received prior radiotherapy must have recovered from toxicity ( $\leq$  grade 2) induced by this treatment. Baseline radiologic scans must be obtained after completion of radiation.

**4.1.16** Patients must complete all screening assessments as outlined in the protocol.

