## 6.6 Cross-over post-progression

Patients who are randomized to enzalutamide alone can crossover to receive enzalutamide + taselisib upon disease progression. Patients who are randomized to enzalutamide alone and who discontinue enzalutamide for toxicity cannot crossover to receive single agent taselisib. However, patients on the enzalutamide + taselisib arm can continue to receive single agent taselisib if they discontinue enzalutamide due to toxicity. Patients who cross over to receive taselisib in combination with enzalutamide will follow the assessments and procedures as outlined in the study calendar. The duration of each cycle will continue to be 28 days and the cycle numbers will "reset" to 1 and will be followed by the "X" suffix (e.g., Cycles 1X, 2X, etc.). Crossover therapy (taselisib) must begin no later than 21 days after the clinic visit at which progression is determined, but can begin as early as C1XD1.

Patients must have labs and procedures performed as outlined in the cross-over study calendar and must meet the values as described in the Inclusion Criteria, prior to receiving taselisib based on assessments and procedures performed within 28 days prior to Day 1 of Cycle 1X. Labs and procedures not included in the cross-over study calendar do not have to be repeated. Patients must also agree to a tumor biopsy, as outlined in the eligibility criteria, prior to initiating taselisib. Patients will receive crossover treatment until progression, intolerable toxicity, or elective withdrawal from the study. Patients who crossover will be evaluated with radiologic assessments every 2 cycles until disease progression.

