#### 11.3.2.2 Pregnancy

The effect of enzalutamide and/or taselisib in pregnant and lactating women is not known, and the exposure of a fetus or nursing infant is considered a potential risk. Enzalutamide and taselisib can cause fetal harm when administered to a pregnant woman based on their mechanism of action. Subjects receiving the study drugs are advised to use 2 acceptable methods of birth control (one of which must include a condom as a barrier method of contraception) starting at the time of screening and continuing throughout the course of treatment and for at least three months after the study drugs are discontinued.

If a female patient or the female partner of a male patient becomes pregnant while receiving investigational therapy or within 30 days after the last dose of investigational product, a pregnancy should be reported to the VICC coordinating center within 24 hours of learning of the pregnancy. As applicable, the investigator should discontinue study drug and counsel the patient, discussing the risks of the pregnancy and the possible effects on the fetus. Monitoring of the patient should continue until conclusion of the pregnancy. Abortion, whether therapeutic or spontaneous, should always be classified as serious, recorded as an SAE, and expeditiously reported to the VICC Coordinating Center. Any congenital anomaly/birth defect in a child born to a female patient or female partner of a male patient exposed to the investigational product should be recorded and reported as an SAE. The expected date of delivery or expected date of the end of the pregnancy, last menstruation, estimated fertility date, pregnancy result and neonatal data etc., should be included in this information.

The Investigator should report the outcome of the pregnancy (independent of outcome, e.g. full term delivery, pre-term delivery, spontaneous abortion, induced abortion, stillbirth, death of newborn, congenital anomaly [including anomaly in a miscarried fetus, etc] in accordance with the same reporting procedure as for SAEs. The date of outcome of the pregnancy, gestational age, date of birth and neonatal data etc., should be included in this information.

VICC Coordinating Center will report such circumstances to Genentech as defined in the Safety and Data Exchange Agreement (SDEA), and to Medivation/Astellas.

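### Entry criterion 4.1.14 binds contraception only from the start of treatment, and the only scheduled pregnancy test may be 28 days old at first dose

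*Combined protocol and SAP*

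**What the plan says.** Section 4.1.14 applies to patients who are neither postmenopausal nor surgically sterile. They must agree to abstinence or to "two adequate methods of contraception (e.g., condoms, diaphragm, vasectomy/vasectomized partner, tubal ligation), during the treatment period". The agreement continues after treatment for 30 days or 3 months, whichever is longer, so in effect 3 months.

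Section 11.3.2.2, in the adverse event reporting chapter, says "Subjects receiving the study drugs are advised to use 2 acceptable methods of birth control (one of which must include a condom"), "starting at the time of screening and continuing throughout the course of treatment" and for at least three months afterwards. The same section says that both drugs can cause fetal harm, judged from their mechanism of action. Section 4.2.7 excludes pregnant women.

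On testing, the main study calendar marks the pregnancy test once, in the screening column. Note j says that "women of child bearing potential must have a negative serum pregnancy test result within 28 days prior to the initial dose of IMP". Note b lists what is done again before dosing: "The following procedures must be repeated at the day 1 visit: Medical and cancer history, physical examination, weight measurement, vital signs, hematology", followed by serum chemistry. Section 4.1.12 adds "Labs are to be repeated on C1D1 and must still meet eligibility", and note h says "Results from labs obtained on C1D1 do have to meet eligibility criteria".

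**The concern.** An entry criterion is what a site checks and documents before registration, because section 5.4 asks for an eligibility checklist with source documents. Advice in a reporting chapter does not have that standing. The protocol itself treats screening as a period that needs contraceptive cover, since 11.3.2.2 says so, but the criterion that controls entry does not carry it.

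The test schedule does not close the gap. A woman can test negative early in screening, conceive, and receive a first dose with no scheduled test in between. What is at stake is an avoidable fetal exposure, and the dosing of a patient whom 4.2.7 means to exclude. No endpoint, sample size or analysis is involved.

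**Working it through.** No statistical figure is in question. The check sets the sections side by side and counts days and tests.

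**When cover starts**
- 4.1.14 (entry criterion): with treatment. The study calendar separates a screening column (Day -28 to Day 1) from the treatment period columns, so the two terms do not overlap in the protocol's own usage.
- 11.3.2.2 (advice): at screening.

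**Age of the test at first dose**
- Age = day of first dose minus day of test. Note j allows 0 to 28 days.
- Days between test and first dose outside the 4.1.14 agreement: the same 0 to 28.
- If 11.3.2.2 is followed, and cover starts no later than the test: 0.

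**Scheduled tests**
- Screening: 1.
- Day 1 repeats under note b: 0. The pregnancy test is not in the list.
- The rule in 4.1.12 that labs be redrawn does not reach it, because that list covers blood counts, liver and renal function, INR and glucose control. Note h defines the clinical laboratory tests without it.

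**First taselisib dose on the combination arm**
- Under note p, taselisib starts on Cycle 2 Day 1, nominally 28 days after enzalutamide. The screening test could then be 28 + 28 = 56 days old.
- The second 28 of those days fall in the treatment period, so 4.1.14 covers them. The time outside the binding agreement stays at 28 days at most.

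**Burden of adding a Cycle 1 Day 1 test**
- Extra blood draws: 0, because blood is already taken that day.
- Extra assays: 1 per woman of childbearing potential. The loose ceiling is the planned phase II maximum in section 15.4, 37 + 12 = 49. The true number is smaller, because some patients will not be of childbearing potential and section 7.2.1.3 shows that phase II has already treated patients. The documents do not give the number of women affected.

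**The case against.** The strongest reply is that the protocol binds as a whole. Sections 4.1.14 and 11.3.2.2 can be satisfied together, and the second already asks for cover from screening. Harm needs a site that enforces one and overlooks the other. History and examination are repeated on Day 1, and note h allows additional tests when clinically appropriate. The consent form may also bind patients from screening; it is not available to us, so its silence cannot be assumed. The 28-day test window matches the general screening window, and no section sets a shorter one.

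Most of this stands, and it limits the point to a gap in what is binding and scheduled. It does not remove that gap. Advice is not an entry condition, and neither a history nor a discretionary test is a scheduled pregnancy test. The protocol already accepts that screening results can go stale, since it redraws other eligibility labs on Day 1.

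A reader might infer more than the documents support:
- **That the two sections contradict each other, or that screening is left without any provision.** They do not, and it is not; 11.3.2.2 reaches that interval.
- **That patients will in fact enroll having agreed to nothing for the screening interval.** That cannot be said without the consent form.
- **That a condom should be mandatory.** It is one example in 4.1.14 and required within the advice in 11.3.2.2, but nothing shows that a pair such as tubal ligation plus a vasectomized partner, both named in 4.1.14, protects less.
- **That the missing tests in later cycles and at crossover are part of the same gap.** The crossover calendar has no pregnancy test, and section 6.6 says "Labs and procedures not included in the cross-over study calendar do not have to be repeated". By then, however, the 4.1.14 agreement is in force.

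**Conclusion.** The point holds in a limited form. Under the eligibility criteria and calendar as written, a conception between the screening test and first dose, an interval of 0 to 28 days, is outside the binding contraception agreement and is not looked for by any scheduled test. If patients follow the advice in 11.3.2.2 from the time of the test, the uncovered interval is 0 days.

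This rests on reading the treatment period in 4.1.14 as the calendar uses it, and on the visible text only. The probability of such a conception cannot be estimated from the documents. It is a participant safety improvement worth making because it costs little, with no bearing on the efficacy analysis.

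**What to change.** At the next amendment:

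1. Change 4.1.14 so that the agreement to abstinence or two adequate methods runs from screening until 3 months after the last dose of study drug. The end point is in effect unchanged, and the bar on hormone-based oral contraceptives stays.
2. Have 11.3.2.2 refer to 4.1.14 instead of setting its own terms, and settle the condom wording one way or the other in the process.
3. Add a serum pregnancy test to the Cycle 1 Day 1 labs in the calendar and note j for women of childbearing potential, with a negative result required before the first dose.

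The first change lowers the chance of conception during screening, and the third is needed to detect one. A Day 1 test can still miss a very recent conception, so the two belong together and neither removes the risk entirely.

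The cost is one assay per woman of childbearing potential on a draw already required, and a contraception commitment that starts up to 28 days earlier. Sites must have the result before dosing, but they already need that day's hematology and chemistry to confirm eligibility.

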### 11.3.3 IND Safety Reports Unrelated to This Trial

IND safety reports not occurring on this trial but involving the study intervention (outside SAEs) received from outside sources will be reviewed by the Protocol Chair and will be forwarded to participating sites for submission to their Institutional Review Boards per their guidelines.

### 11.3.4 Institutional Review Board

All adverse events and serious adverse events will be reported to the participating institution's IRB per current institutional standards. If an adverse event requires modification of the informed consent, these modifications will be provided to the IRB with the report of the adverse event. If an adverse event requires modification to the study protocol, these modifications will be provided to the IRB as soon as is possible.

### 11.3.5 Food and Drug Administration (FDA)

Vanderbilt will report to the FDA any adverse event that is serious, unexpected and reasonably related (i.e., possible, probable, definite) to the study treatment.

Unexpected fatal or life-threatening experiences associated with the use of the study treatment will be reported to FDA as soon as possible but in no event later than 7 calendar days after initial receipt of the information.

All other serious unexpected experiences associated with the use of the study treatment will be reported to FDA as soon as possible but no later than 15 calendar days after initial receipt of the information.

Events will be reported to the FDA by telephone ([name]) or by [contact]) using Form FDA 3500A (Mandatory Reporting Form for investigational agents).

### 11.3.6 Genentech

All SAEs must be reported to the Coordinating Center (Vanderbilt) within 24 hours. Vanderbilt will report all SAEs regardless of causal relationship to study treatment using the MedWatch form (using the online form available at <http://www.fda.gov/safety/medwatch/howtoreport/default.htm>) to Genentech as defined in the Safety and Data Exchange Agreement (SDEA). If the SAE is linked to taselesib only, the form will only be submitted to Genentech.

### 11.3.7 Medivation/Astellas

All SAEs must be reported to the Coordinating Center (Vanderbilt) within 24 hours. Vanderbilt will report all SAEs related to enzalutamide to Astellas using the Medwatch form (using the online form available at <http://www.fda.gov/safety/medwatch/howtoreport/default.htm>). The Investigator will submit a copy of this MedWatch form to Astellas by either e-mail or fax, within the same timeframe. If submission of this SAE to FDA or Astellas or is not possible within 24 hours, the Investigator's local drug safety contact (IRB, etc.) should be informed by phone. If the SAE is linked to enzalutamide only, the form will only be submitted to Astellas.

The SAE documentation, including the Medwatch 3500A Form and available source records should be emailed or faxed to:

[REDACTED]

The following minimum information is required:

- Study number/IIT regulatory identifier
- Subject number, sex and age
- The date of report
- A description of the SAE (event, seriousness of the event)
- Causal relationship to the study drug

Follow-up information for the event should be sent within promptly (within 7 days) as necessary.

